## 8.6 Other Analyses

### 8.6.1 Sweat Chloride

Sweat chloride (SwCl): the SwCl value for a given visit will be calculated as the mean of the non-missing sweat chloride measurements obtained on the left and right arms at that visit. If one of the two arm measurements at a time point is missing, the other will be used as the mean. A volume  $\geq 15$   $\mu\text{L}$  is required for an accurate determination of sweat chloride. Any results reported as having volume  $< 15$   $\mu\text{L}$  will be considered missing for analysis purposes. Any sweat chloride

values reported as <10 mmol/L or >160 mmol/L will be considered missing for analysis purposes.

#### **Clinic collected Sweat Chloride data**

Clinic collected SwCl values and change from SwCl baseline will be summarized using descriptive statistics by genotype (i.e. F/MF and F/F) at each visit for Part A and B respectively based on the Safety Set.

#### **Home collected Sweat chloride data**

Home collected SwCl values will be summarized using descriptive statistics for subjects with valid home collected SwCl values (a subset of approximately 50 subjects). Average will be taken for a subject if the subject has more than 1 valid home collected SwCl values collected at different unscheduled visits. In addition, the clinic collected sweat chloride at the scheduled visits will also be summarized for the same subset of subjects.

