**Table 3-1 VX18-445-113: Treatment Period and Safety Follow-up Visit**

Event/Assessment a	Treatment Period							ETT Visit b	Safety Follow-up Visit (28 ± 7 Days After Last Dose) c	Comments
	Day 1 d	Day 15 (± 3 Days)	Weeks 4, 8, 16, 24, 36 (± 5 Days)	Weeks 12, 20, 28, 32, 40, 44, 52, 56, 64, 68, 76, 80, 88, 92 (± 5 Days)	Week 48 (± 5 Days)	Weeks 60, 72, 84 (± 5 Days)	Week 96 (± 5 Days)			
Ophthalmologic examination					X		X	X	X	Subjects <18 years of age on the date of informed consent in the parent studies of Study 659-105 will have an ophthalmologic examination within 28 days of the Week 48 and Week 96 Visits. In addition, an ophthalmologic examination will be performed within 28 days of the ETT Visit for subjects who prematurely discontinue study drug if the subject has received at least 12 weeks of study drug since their last ophthalmologic examination. (Section 11.4.7).
Complete physical examination	X						X	X		Section 11.4.3
Pregnancy test	Urine		Urine	Urine	Urine	Urine	Serum	Serum	Serum	All female subjects (Section 11.4.2)
FSH										As needed for any suspected postmenopausal female with at least 12 months of continuous spontaneous amenorrhea (Section 11.4.2)
Standard 12-lead ECG	X	X	Weeks 8, 24		X	Week 72	X	X	X	After subjects have rested for at least 5 minutes and before dosing, as applicable (Sections 11.4.3, 11.4.5, and 11.4.6)
Vital signs	X	X	X		X	X	X	X	X	
Pulse oximetry	X	X	X		X	X	X	X	X	
Spirometry	X	X	X		X	X	X	X	X	Section 11.4.8
SwCl			Week 24				X	X		Approximately 50 subjects may participate in 1 to 2 additional, optional sweat tests at unscheduled home visits (Section 11.5.1)
Urinalysis	X				X		X	X	X	Section 11.4.2

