## 11.5 Other Assessments

### 11.5.1 Sweat Chloride

SwCl samples will be collected with an approved collection device. Each collection will occur before study drug dosing (Section 9.6.1). At each time point, 2 samples will be collected, 1 from each arm (left and right). Sweat samples will be sent to a central laboratory for testing and interpretation of results. Specific instructions for the collection, handling, processing, and shipping of SwCl samples to the central laboratory will be provided separately.

To assess the feasibility of home-based sweat collection, approximately 50 subjects may participate in 1 to 2 additional, optional sweat tests. At this unscheduled home visit, 2 samples will be collected, 1 from each arm (left and right). Sweat samples will be sent to a central laboratory for testing and interpretation of results.

Subjects (and their parents/caregivers/companions) should not be informed of their study-related SwCl results until Vertex has determined that the study has been completed (i.e., CSR finalization), regardless of whether the subject has prematurely discontinued treatment.

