## 11 APPENDICES

### Appendix A: Analysis Visit Windows for Safety Assessments

Table 11-1 Analysis Visit Windows for Safety Assessments			
Assessment	Visit	Target Study Day	Analysis Visit Window (in study days)
Part A			
Spirometry Serum Chemistry Hematology Vital Signs  Pulse Oximetry	Baseline	1	defined in section 8.1
	Day 15	15	[1, 22] where day 1 is post-dose measurement
	Week 4	29	(22, 43]
	Week 8	57	(43, 85]
	Week 16	113	(85, 141]
	Week 24	169	(141, 211]
	Week 36	253	(211, 295]
	Week 48	337	(295, 379]
	Week 60	421	(379, 463]
	Week 72	505	(463, 547]
	Week 84	589	(547, 631]
	Week 96	673	(631, 687]
	Safety Follow-up 	Not applicable	Use nominal visit
Standard 12-lead ECG	Baseline	1	defined in section 8.1
	Day 15	15	[1, 36] where day 1 is post-dose measurement
	Week 8	57	(36, 113]
	Week 24	169	(113, 253]
	Week 48	337	(253, 421]
	Week 72	505	(421, 589]
	Week 96	673	(589, 687]
	Safety Follow-up 	Not applicable	Use nominal visit
Coagulation	Baseline	1	defined in section 8.1
	Week 24	169	[1, 253] where day 1 is post-dose measurement
	Week 48	337	(253, 421]
	Week 72	505	(421, 589]
	Week 96	673	(589, 687]
		Safety Follow-up 	Not applicable

Table 11-1 Analysis Visit Windows for Safety Assessments			
Assessment	Visit	Target Study Day	Analysis Visit Window (in study days)
Weight, Height and BMI	Baseline	1	defined in section 8.1 [1, 43] where day 1 is post-dose measurement (43, 85] (85, 141] (141, 211] (211, 295] (295, 379] (379, 463] (463, 547] (547, 631] (631, 687] Use nominal visit
	Week 4	29	
	Week 8	57	
	Week 16	113	
	Week 24	169	
	Week 36	253	
	Week 48	337	
	Week 60	421	
	Week 72	505	
	Week 84	589	
	Week 96	673	
	Safety Follow-up 	Not applicable	
Sweat Chloride (Clinic collected only)	Baseline	--	defined in section 8.1 [1, 421] where day 1 is post-dose measurement (421, 687]
	Week 24	169	
	Week 96	673	
Sweat Chloride (collected at unscheduled home visits)	Home SwCl collection visit 1	Not applicable	Use nominal visit 
	Home SwCl collection visit 2	Not applicable	Use nominal visit 
Part B			
Spirometry Serum Chemistry Hematology Vital Signs  Weight, Height and BMI Pulse Oximetry	Baseline	--	defined in section 8.1 [1, 127] where day 1 is post-dose measurement (127, 211] (211, 295] (295, 351] Use nominal visit
	Part B Week 12	85	

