	Part B Week 24	169	
	Part B Week 36	253	
	Part B Week 48	337	
	Part B Safety Follow-up 	Not applicable	
Standard 12-lead ECG	Baseline	--	defined in section 8.1 [1, 127] where day 1 is post-dose measurement (127, 253] (253, 351] Use nominal visit
	Part B Week 12	85	
	Part B Week 24	169	
	Part B Week 48	337	
	Part B Safety Follow-up 	Not applicable	
Coagulation	Baseline	--	defined in section 8.1 [1, 253] where day 1 is post-dose measurement (253, 351] Use nominal visit
	Part B Week 24	169	
	Part B Week 48	337	
	Part B Safety Follow-up 	Not applicable	
Sweat Chloride 	Baseline	--	Defined in section 8.1 [1, 253] where day 1 is post-dose measurement (253, 351]
	Part B Week 24	169	
	Part B Week 48	337	

Notes:

 Visit name for analysis purpose is used to report data in tables and figures.

 The analysis visit windows will be applied using the following rules for both scheduled and unscheduled visits except for SwCl collected at unscheduled home visits:

1. If no numerical measurement is available within a visit window, the measurement will be considered missing for the visit.
2. If there is more than 1 numerical measurement available within a visit window, use the following rules:
  - i. The measurement closest to the target day will be used; or
  - ii. If there are multiple measurements with the same distance from the target day, the latest measurement will be used. If the latest measurement cannot be determined, then unscheduled visit will be selected.

 For measurement collected on the date of first dose of study drug in Treatment Period, if it cannot be determined whether the measurement is before or after the first dose:

1. Scheduled measurement will be treated as pre-dose observation.
2. Unscheduled measurement will be treated as post-dose observation.

 For safety Assessment, Safety Follow-up analysis visit will be based on nominal Safety Follow-up visit. If a subject doesn't have a nominal Safety Follow-up visit but has an ETT visit with study day >687 for Part A or >351 for Part B, then the ETT visit will be mapped into Safety Follow-up analysis visit for the corresponding part.

 If one subject has multiple home collected SwCl samples at different unscheduled visits, the assignment of the visits will be based on chronological order.

Derived Variables for each part:

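### Home and clinic sweat chloride are summarized side by side in the same subset, but no within-subject difference is planned, so the tables cannot show individual agreement or the precision of any average difference.

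*SAP*

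**What the plan says.** Protocol 11.5.1 gives the purpose of the home samples: "To assess the feasibility of home-based sweat collection, approximately 50 subjects may participate in 1 to 2 additional, optional sweat tests." The comment in Protocol Table 3-1 places these tests at unscheduled home visits. The same table schedules clinic sweat chloride at Week 24, Week 96 and the Early Termination of Treatment Visit. Protocol 12.3.4 leaves the sweat chloride analysis to the SAP.

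SAP 8.6.1 first summarizes clinic values by genotype at each visit for the whole Safety Set. For the home samples it plans descriptive statistics in subjects with a valid home value. On repeat samples it says: "Average will be taken for a subject if the subject has more than 1 valid home collected SwCl values collected at different unscheduled visits." It then adds the comparator: "In addition, the clinic collected sweat chloride at the scheduled visits will also be summarized for the same subset of subjects."

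SAP Appendix A, Table 11-1, lists home collection visits 1 and 2 as separate nominal visits. For a subject with several home samples, "the assignment of the visits will be based on chronological order." The notes to that table keep home samples out of the windowing: "The analysis visit windows will be applied using the following rules for both scheduled and unscheduled visits except for SwCl collected at unscheduled home visits." In Part A the clinic windows run from day 1 to day 421 for Week 24, and from after day 421 to day 687 for Week 96.

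Neither document specifies a home-minus-clinic difference within a subject, an SD of differences, limits of agreement, a confidence interval for the difference, or a rule for choosing which clinic sample goes with a home sample.

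**The concern.** Clinic values are already summarized for the whole Safety Set. Repeating that summary for the home subset has little use except to set clinic results beside home results. Yet the plan stops at two group summaries, although each subject is expected to contribute both kinds of sample.

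Two similar means can conceal large disagreement in individuals. Two different means can arise because the samples were taken months apart, or because some clinic samples are missing. Averaging over home visits adds a further mismatch, because each clinic figure comes from a single visit. At stake is what can be concluded from the home samples: the data to describe agreement would be collected, but the planned output would not describe it.

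**Working it through.** **Inputs.** From the documents: about 50 subjects, one or two home tests each, a per-visit value that is the mean of both arms, unscheduled home visits, and clinic samples at Week 24, Week 96 or early termination. The documents give no SD, home-clinic correlation or within-person SD for sweat chloride, and no precision target for the subset, so there is no plan figure to reproduce. Everything below rests on assumed values.

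**1. Do two marginal summaries fix individual agreement?** Let home and clinic values have the same mean and the same SD s, with correlation r.

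- SD of paired differences = s × √(2(1 − r))
- 95% limits of agreement = mean difference ± 1.96 × SD of differences
- 95% CI half-width for the mean difference = t(49) × SD of differences / √50
- 95% CI half-width for each limit = t(49) × SD of differences × √(1/50 + 1.96²/(2 × 49))

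For s = 15 mmol/L and n = 50 (all in mmol/L):

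| r | SD of differences | Limits of agreement | CI half-width, mean difference | CI half-width, each limit |
|---|---|---|---|---|
| 0 | 21.2 | ±41.6 | 6.0 | 10.4 |
| 0.5 | 15.0 | ±29.4 | 4.3 | 7.3 |
| 0.8 | 9.5 | ±18.6 | 2.7 | 4.6 |
| 0.95 | 4.7 | ±9.3 | 1.3 | 2.3 |

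The planned tables would look the same in all four rows, because they do not contain r. Over s = 10 to 20 and r = 0 to 0.95, the limits run from ±6.2 to ±55.4. The precision of the mean difference is equally undetermined.

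**2. Can the average difference be read off?** If every subject in the subset has a clinic value at the visit shown, the difference of the two means equals the mean of the paired differences. So average bias can be hinted at, without a confidence interval. If clinic values are missing, the two means rest on different numbers of subjects and the equality fails.

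**3. What does averaging two home visits do?** There are two separate effects.

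- *Total home SD.* Assume between-subject SD 20 and single-visit within-subject SD w. The SD falls from √(400 + w²) to √(400 + w²/2). For w = 6 it goes from 20.9 to 20.4, about 2%. For w = 12 it goes from 23.3 to 21.7, about 7%. This supposes that every subject has two valid home values.
- *Spread of differences.* If home and clinic errors are equal and independent, the SD of the difference is √2 × w for a single home value and √1.5 × w for an averaged one. The ratio is √(1.5/2) = 0.866. For w = 8 the limits are ±22.2 with single values and ±19.2 with averaged ones. With a mix of one and two home values the ratio lies between 0.866 and 1.

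The first effect is slight. The second matters once differences are taken, because averaged values understate the disagreement of a single home sample.

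**4. Timing.** SAP 6.1 dates the amendment that added home collection to March 2021, and version 1.0 of the protocol is dated May 2019. The documents give no enrolment or home-visit dates, so the actual gaps are unknown. Since no window ties a home sample to a clinic sample, nothing limits the gap, and a difference in means mixes collection setting with elapsed time.

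**The case against.** The strongest reply is that the aim is feasibility. Sweat chloride is only the other endpoint, the home samples are optional, and no agreement or replacement objective is stated anywhere. Leaving out limits of agreement is therefore not a failure against a declared aim. This stands, and it keeps the point minor. The choice to repeat the clinic summary for this subset still shows that a comparison is intended.

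Four stronger readings are tempting, and the documents do not support them.

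- *The home samples cannot show agreement.* The limit is in the planned tables. The paired data would exist and could be analysed.
- *The two summaries cover different people.* SAP 8.6.1 restricts both to the same subset. Missing clinic samples can reduce n, but n is one of the summary statistics listed in SAP 8.1, so a shortfall would be visible.
- *Averaging makes the home SD misleadingly small.* Within-subject SD does fall by 1 − 1/√2 = 29% when two visits are averaged, but total SD falls only about 2% to 7% under the assumptions above.
- *The plan gives a much less precise home-clinic comparison than pairing would.* The SAP plans no standard error or interval for a difference. Treating the two summaries as independent samples would be a reader's own construction.

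A further reply is that Table 11-1 keeps home visits 1 and 2 apart, so visit-level values are not lost. That is right and makes the fix easier, although the SAP does not say which output uses the separate visits and which uses the average. Finally, pairing does not by itself remove the effect of elapsed time. That also stands, and it is why the pairing rule needs a maximum gap.

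**Conclusion.** The point holds as a low-cost improvement to a secondary, feasibility-driven part of the plan. It does not touch the primary safety objective.

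The planned summaries can at most hint at an average home-clinic difference when data are complete. They give no precision for it and no information on agreement within a person. Under an assumed common SD of 15 mmol/L, identical tables are compatible with limits of agreement from about ±9 to about ±42 mmol/L. Averaging two home visits changes the total home SD little, but would shrink the spread of home-clinic differences to about 0.87 of the single-sample value if errors are equal and independent and every subject has two home values. All SDs and correlations are assumptions. The structural conclusion, that two marginal summaries do not determine paired agreement, does not depend on them.

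**What to change.** In SAP 8.6.1, add a within-subject home-minus-clinic difference:

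- Use each home visit's own value, not the average. Table 11-1 already separates visits 1 and 2.
- Pair it with the nearest on-treatment clinic value within a maximum number of days stated in advance. Show all pairs regardless of gap as a sensitivity analysis.
- Allow for two home values from one subject, for example by taking home visit 1 as the main pair.
- Report the number of pairs, the mean difference with 95% CI, the SD of differences, the 95% limits of agreement and the days between samples.
- Keep the planned group summaries as supportive.

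The cost is some SAP wording and one small table, with no new samples or visits. SAP section 3 allows amendment before database lock and requires later changes to be documented in the study report. Fixing the pairing rule in advance also avoids choosing the clinic comparator after the data are seen. The downside is fewer pairs if few clinic samples fall within the permitted gap.

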## **9 INTERIM AND DMC ANALYSES**

### **9.1 Interim Analysis**

IA may take place at any time during the study at the discretion of the sponsor.

### **9.2 IDMC Analysis**

The IDMC's objectives and operational details will be defined in a separate document (IDMC Charter) which was finalized before the first subject first visit. The IDMC's planned safety reviews of study data are outlined in the IDMC Charter and IDMC Statistical Analysis Plan.

## 11 APPENDICES

### Appendix A: Analysis Visit Windows for Safety Assessments

Table 11-1 Analysis Visit Windows for Safety Assessments			
Assessment	Visit	Target Study Day	Analysis Visit Window (in study days)
Part A			
Spirometry Serum Chemistry Hematology Vital Signs  Pulse Oximetry	Baseline	1	defined in section 8.1
	Day 15	15	[1, 22] where day 1 is post-dose measurement
	Week 4	29	(22, 43]
	Week 8	57	(43, 85]
	Week 16	113	(85, 141]
	Week 24	169	(141, 211]
	Week 36	253	(211, 295]
	Week 48	337	(295, 379]
	Week 60	421	(379, 463]
	Week 72	505	(463, 547]
	Week 84	589	(547, 631]
	Week 96	673	(631, 687]
	Safety Follow-up 	Not applicable	Use nominal visit
Standard 12-lead ECG	Baseline	1	defined in section 8.1
	Day 15	15	[1, 36] where day 1 is post-dose measurement
	Week 8	57	(36, 113]
	Week 24	169	(113, 253]
	Week 48	337	(253, 421]
	Week 72	505	(421, 589]
	Week 96	673	(589, 687]
	Safety Follow-up 	Not applicable	Use nominal visit
Coagulation	Baseline	1	defined in section 8.1
	Week 24	169	[1, 253] where day 1 is post-dose measurement
	Week 48	337	(253, 421]
	Week 72	505	(421, 589]
	Week 96	673	(589, 687]
		Safety Follow-up 	Not applicable

Table 11-1 Analysis Visit Windows for Safety Assessments			
Assessment	Visit	Target Study Day	Analysis Visit Window (in study days)
Weight, Height and BMI	Baseline	1	defined in section 8.1 [1, 43] where day 1 is post-dose measurement (43, 85] (85, 141] (141, 211] (211, 295] (295, 379] (379, 463] (463, 547] (547, 631] (631, 687] Use nominal visit
	Week 4	29	
	Week 8	57	
	Week 16	113	
	Week 24	169	
	Week 36	253	
	Week 48	337	
	Week 60	421	
	Week 72	505	
	Week 84	589	
	Week 96	673	
	Safety Follow-up 	Not applicable	
Sweat Chloride (Clinic collected only)	Baseline	--	defined in section 8.1 [1, 421] where day 1 is post-dose measurement (421, 687]
	Week 24	169	
	Week 96	673	
Sweat Chloride (collected at unscheduled home visits)	Home SwCl collection visit 1	Not applicable	Use nominal visit 
	Home SwCl collection visit 2	Not applicable	Use nominal visit 
Part B			
Spirometry Serum Chemistry Hematology Vital Signs  Weight, Height and BMI Pulse Oximetry	Baseline	--	defined in section 8.1 [1, 127] where day 1 is post-dose measurement (127, 211] (211, 295] (295, 351] Use nominal visit
	Part B Week 12	85	
	Part B Week 24	169	
	Part B Week 36	253	
	Part B Week 48	337	
	Part B Safety Follow-up 	Not applicable	
Standard 12-lead ECG	Baseline	--	defined in section 8.1 [1, 127] where day 1 is post-dose measurement (127, 253] (253, 351] Use nominal visit
	Part B Week 12	85	
	Part B Week 24	169	
	Part B Week 48	337	
	Part B Safety Follow-up 	Not applicable	
Coagulation	Baseline	--	defined in section 8.1 [1, 253] where day 1 is post-dose measurement (253, 351] Use nominal visit
	Part B Week 24	169	
	Part B Week 48	337	
	Part B Safety Follow-up 	Not applicable	
Sweat Chloride 	Baseline	--	Defined in section 8.1 [1, 253] where day 1 is post-dose measurement (253, 351]
	Part B Week 24	169	
	Part B Week 48	337	

Notes:

 Visit name for analysis purpose is used to report data in tables and figures.

 The analysis visit windows will be applied using the following rules for both scheduled and unscheduled visits except for SwCl collected at unscheduled home visits:

1. If no numerical measurement is available within a visit window, the measurement will be considered missing for the visit.
2. If there is more than 1 numerical measurement available within a visit window, use the following rules:
  - i. The measurement closest to the target day will be used; or
  - ii. If there are multiple measurements with the same distance from the target day, the latest measurement will be used. If the latest measurement cannot be determined, then unscheduled visit will be selected.

 For measurement collected on the date of first dose of study drug in Treatment Period, if it cannot be determined whether the measurement is before or after the first dose:

1. Scheduled measurement will be treated as pre-dose observation.
2. Unscheduled measurement will be treated as post-dose observation.

 For safety Assessment, Safety Follow-up analysis visit will be based on nominal Safety Follow-up visit. If a subject doesn't have a nominal Safety Follow-up visit but has an ETT visit with study day >687 for Part A or >351 for Part B, then the ETT visit will be mapped into Safety Follow-up analysis visit for the corresponding part.

 If one subject has multiple home collected SwCl samples at different unscheduled visits, the assignment of the visits will be based on chronological order.

Derived Variables for each part:

1. Age (in years) at first dose date and post-baseline visit (for demographics, listing and the calculation of [percent] predicted spirometry variables):

Obtain the age at informed consent in "yy, mm" format (e.g., 24 years, 6 months) from the Vital Signs (VS) page at the Day 1 Visit and add 0.5 month to convert to days.

Obtain the informed consent date.

Then age (in years) at first dose or post-baseline visit = [(first dose date or post-baseline visit date – informed consent date) in days + age at informed consent (in days)]/365.25.

2. Missing first dose date or last dose date

If the first dose date is missing, use Day 1 visit date.

If the last dose date of study drug is not available and there is no data to indicate that the subject discontinued treatment, the data cutoff date will be used instead.

If the subject discontinued treatment and the last dose date is missing or partial date is reported, the last dose date will be imputed based on, in descending order priority, the Early Treatment Termination (ETT) visit date, last visit date before the Safety Follow-up, or the last study drug administration date from EX SDTM domain, as appropriate. The imputation algorithm will ensure the imputed last dose date does not exceed the data cutoff date.

3. Electrocardiogram:

Baseline is defined in Section 8.1. If multiple ECG measurements are obtained on the same calendar day during the TE period,

- For summary purpose, the average value will be used as the ECG on that day;
- For threshold analysis purpose, all ECG values will be used

